### 6.2.2. Study Day and Reference Dates

The safety reference date is the study intervention start date and will be used to calculate study day for safety measures.

The study day is calculated as below:

Assessment Date = Missing → Study Day = Missing

Assessment Date < Reference Date → Study Day = Assessment Date – Ref Date

Assessment Date ≥ Reference Date → Study Day = Assessment Date – Ref Date + 1

### 6.2.3. Assessment Window

Different body weight will have different schedule of visits. Therefore, the data will be analysed by the analysis timepoint (Week 0, Week 2, Week 4, Week 6, Week 8, Week 10, Week 12, 8-week Follow-up and 16-week Follow-up).

Early withdrawal and unscheduled visits will be slotted to the appropriate planned visit. The assigned analysis timepoint will be based on the interval in which the Study Day for the early withdrawal or unscheduled visit falls according to intervals provided below.

**Body weight  $\geq$ 50 kg, Dose 200 mg QW**

Analysis Set / Domain	Target	Analysis Window		Analysis Timepoint
		Beginning Timepoint	Ending Timepoint	
All	Day-1	na	na	Screening (Visit 1)
All	Day 1	na	na	Visit 2 (Week 0)
All	Day 4	Day 2	Day 5	Visit 3
All	Day 8	Day 6	Day 11	Visit 4
All	Day15	Day 12	Day 18	Visit 5 (Week 2)
All	Day 22	Day 19	Day 25	Visit 6
All	Day 29	Day 26	Day 32	Visit 7 (Week 4)
All	Day 36	Day 33	Day 39	Visit 8
All	Day 43	Day 40	Day 46	Visit 9 (Week 6)
All	Day 50	Day 47	Day 53	Visit 10
All	Day 57	Day 54	Day 60	Visit 11 (Week 8)
All	Day 64	Day 61	Day 67	Visit 12
All	Day 71	Day 68	Day 74	Visit 13 (Week 10)
All	Day 78	Day 75	Day 79	Visit 14
All	Day 81	Day 80	Day 82	Visit 15
All	Day 85	Day 83	Day 87	Visit 16 (Week 12)
All	Day 141	na	na	Visit 17 (8 week Follow-up)
All	Day 197	na	na	Visit 18 (16 week Follow-up)

**NOTES:**

- If there are multiple assessments within the same window, a scheduled visit will be prioritized over unscheduled visits. If all assessments within the same window are from unscheduled visits, the earliest one will be taken in the slotting.

**Body weight  $\geq$ 30 kg -  $<$ 50 kg, Dose 200 mg Q10d**

Analysis Set / Domain	Target	Analysis Window		Analysis Timepoint
		Beginning Timepoint	Ending Timepoint	
All	Day-1	na	na	Screening (Visit 1)
All	Day 1	na	na	Visit 2 (Week 0)
All	Day 4	Day 2	Day 7	Visit 3
All	Day 11	Day 8	Day 15	Visit 4 (Week 2)
All	Day 21	Day 16	Day 25	Visit 5
All	Day 31	Day 26	Day 35	Visit 6 (Week 4)
All	Day 41	Day 36	Day 45	Visit 7 (Week 6)
All	Day 51	Day 46	Day 55	Visit 8
All	Day 61	Day 56	Day 65	Visit 9 (Week8)
All	Day 71	Day 66	Day 72	Visit 10 (Week 10)
All	Day 74	Day 73	Day 77	Visit 11
All	Day 81	Day 78	Day 84	Visit 12 (Week 12)
All	Day 137	na	na	Visit 13 (8 week Follow-up)
All	Day 193	na	na	Visit 14 (16 week Follow-up)

**NOTES:**

- If there are multiple assessments within the same window, a scheduled visit will be prioritized over unscheduled visits. If all assessments within the same window are from unscheduled visits, the earliest one will be taken in the slotting.

**Body weight ≥15 kg - <30kg, Dose 200 mg Q2W**

Analysis Set / Domain	Target	Analysis Window		Analysis Timepoint
		Beginning Timepoint	Ending Timepoint	
All	Day-1	na	na	Screening (Visit 1)
All	Day 1	na	na	Visit 2 (Week 0)
All	Day 4	Day 2	Day 9	Visit 3
All	Day 15	Day 10	Day 21	Visit 4 (Week 2)
All	Day 29	Day 22	Day 35	Visit 5 (Week 4)
All	Day 43	Day 36	Day 49	Visit 6 (Week 6)
All	Day 57	Day 50	Day 63	Visit 7 (Week 8)
All	Day 71	Day 64	Day 72	Visit 8 (Week 10)
All	Day 74	Day 73	Day 79	Visit 9
All	Day 85	Day 80	Day 90	Visit 10 (Week 12)
All	Day 141	na	na	Visit 11 (8 week Follow-up)
All	Day 197	na	na	Visit 12 (16 week Follow-up)

**NOTES:**

- If there are multiple assessments within the same window, a scheduled visit will be prioritized over unscheduled visits. If all assessments within the same window are from unscheduled visits, the earliest one will be taken in the slotting.

**6.2.4. Multiple measurements at One Analysis Time Point**

For lab tests on a study day, if more than one assessment is taken on the same day, the test from a central lab will be taken over the test from a local lab. If multiple assessments are taken from the same type of lab, the worst case will be used.

**6.2.5. Handling of Partial Dates**

Element	Reporting Detail			
General	
 
• Partial dates will be displayed as captured in participant listing displays.
 
• However, where necessary, display macros may impute dates as temporary variables for sorting data in listings only. In addition, partial dates may be imputed for 'slotting' data to study phases or for specific analysis purposes as outlined below.
 
• Imputed partial dates will not be used to derive study day, time to onset or duration (e.g., time to onset or duration of adverse events), or elapsed time variables (e.g., time since diagnosis). In addition, imputed dates are not used for deriving the last contact date in overall survival analysis dataset.
 
			
Adverse Events	
 
• Partial dates for AE recorded in the CRF will be imputed using the following conventions:           
 
 Missing start day	           If study intervention start date is missing (i.e. participant did not start study intervention), then set start date = 1st of month.            Else if study intervention start date is not missing:           
 
• If month and year of start date = month and year of study intervention start date, then               
 
– If stop date contains a full date and stop date is earlier than study intervention start date, then set start date= 1st of month.
 
 
 
 	
 
 
 
		Missing start day	If study intervention start date is missing (i.e. participant did not start study intervention), then set start date = 1st of month. Else if study intervention start date is not missing: 
 
• If month and year of start date = month and year of study intervention start date, then               
 
– If stop date contains a full date and stop date is earlier than study intervention start date, then set start date= 1st of month.
 
 
 

Missing start day	If study intervention start date is missing (i.e. participant did not start study intervention), then set start date = 1st of month. Else if study intervention start date is not missing: 
 
• If month and year of start date = month and year of study intervention start date, then               
 
– If stop date contains a full date and stop date is earlier than study intervention start date, then set start date= 1st of month.
 
 
 
			

Element	Reporting Detail
	
– Else set start date = study intervention start date.
 
Else set start date = 1st of month.
 
Missing start day and month
 
If study intervention start date is missing (i.e. participant did not start study intervention), then set start date = January 1.
 
Else if study intervention start date is not missing:
 
 
• If year of start date = year of study intervention start date, then 
 
– If stop date contains a full date and stop date is earlier than study intervention start date, then set start date = January 1.
 
– Else set start date = study intervention start date.
 
 
 
 
Else set start date = January 1.
 
Missing end day
 
A '28/29/30/31' will be used for the day (dependent on the month and year).
 
Missing end day and month
 
No Imputation
 
Completely missing start/end date
 
No imputation

Concomitant Medications/Medical History	
 
• Partial dates for any concomitant medications recorded in the CRF will be imputed using the following convention:
 
 
Missing start day
 
If study intervention start date is missing (i.e. participant did not start study intervention), then set start date = 1st of month.
 
Else if study intervention start date is not missing:
 
 
• If month and year of start date = month and year of study intervention start date, then 
 
– If stop date contains a full date and stop date is earlier than study intervention start date, then set start date= 1st of month.
 
– Else set start date = study intervention start date.
 
 
 
 
Else set start date = 1st of month.

	
Missing start day and month
 
If study intervention start date is missing (i.e. participant did not start study intervention), then set start date = January 1.
 
Else if study intervention start date is not missing:
 
 
• If year of start date = year of study intervention start date, then 
 
– If stop date contains a full date and stop date is earlier than study intervention start date, then set start date = January 1.
 
– Else set start date = study. intervention start date.
 
 
 
 
Else set start date = January 1.

	
Missing end day
 
A '28/29/30/31' will be used for the day (dependent on the month and year).

Element	Reporting Detail	
	Missing end day and month	A '31' will be used for the day and 'Dec' will be used for the month.
	Completely missing start/end date	No imputation

### 6.2.6. SLE Allowable Medication Categories at Baseline

Medication Category	Rule
Anti-malarials	Set to Anti-malarial if LISTCODE = 332735 and the route of administration is not 'TOPICAL', 'VAGINAL', 'CONJUNCTIVAL', 'INTRANASAL', 'INHALATION', 'INTRA-OCULAR', 'INTRATRACHEAL', 'EPIDURAL', 'INTRAARTICULAR', 'OTHER'.
Steroids	Set to Steroids if LISTCODE = 30000010N, and the route of administration is "INTRADERMAL", "INTRAMUSCULAR", "INTRAVENOUS", "ORAL", "SUBCUTANEOUS" or "INTRA-ARTICULAR".
Immunosuppressants	Set to Immunosuppressants if TOILIST.LISTCODE = 333236, and the route of administration is not "TOPICAL". Or CMDECOD contains "MERCAPTOPURINE", and the route of administration is in 'ORAL'. Or CMDECOD contains "CYCLOPHOSPHAMIDE", and the route of administration is 'ORAL' or 'PARENTERAL'.
NSAIDs	Set to NSAIDS if LISTCODE = 30001761N.
Aspirins	Set to Aspirin if LISTCODE = 332752.
General rules	
If CMATCCD contains "V90", set to null.
 
If both "ANTIMALARIALS" and 'IMMUNOSUPPRESSANTS' definition is satisfied, define "ANTIMALARIALS" prior to 'IMMUNOSUPPRESSANTS'.
 
If both "ASPIRIN" and 'NSAIDS' definition is satisfied, define "ASPIRIN" prior to 'NSAIDS'.
 
If CMCAT1='IMMUNOSUPPRESSANTS' and CMDECOD='CICLOSPORIN' and CMROUTE='INTRAOCULAR' then set to null.

Adjudication is performed.

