4.4. End of Study Definition

A participant is considered to have completed the study if he/she has completed treatment phase (12 weeks) of the study.

The end of the study is defined as the date of the last assessment (16-week post-treatment follow-up) of the last participant in the study.

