6.6. Continued Access to Study Intervention after the End of the Study

Following the end of treatment at Week 12 or early withdrawal from the study, the participant will follow standard of care for SLE as determined by the investigator.

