6.8.2. Prohibited Concomitant Therapy

Participants who start prohibited medications or therapies at any time during the study will be considered a protocol violation. Belimumab will be discontinued and participants will be withdrawn from the study.

The following medications and therapies are prohibited at any time during the study:

- Other investigational agents (biologic or non-biologic). Investigational applies to any drug not approved for sale in the country in which it is being used.
- Participation in a study using an investigational agent or non-drug therapy that may interfere with the conduct of this protocol (except study 213560)

- Anti- Tumor Necrosis Factor (TNF) or anti-IL-6 therapy (e.g., adalimumab, etanercept, infliximab, certolizumab, tocilizumab, golimumab).
- All biologics (e.g., rituximab, abatacept, interleukin-1 receptor antagonist).
- Janus kinase (JAK) inhibitors.
- Intravenous immunoglobulin (IVIG).
- IV cyclophosphamide (oral cyclophosphamide is permitted).
- Plasmapheresis, leukapheresis.
- Any live or live attenuated vaccines. (Participants who require a live or live attenuated vaccine during the study should have belimumab discontinued prior to receiving the vaccine).

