### 6.2.7. Prohibited Medications and Non-Drug Therapies

Participants who start prohibited medications or therapies at any time during the study will be considered a protocol violation. Belimumab will be discontinued, and participants will be withdrawn from the study.

The following medications and therapies are prohibited at any time during the study:

- Other investigational agents (biologic or non-biologic). Investigational applies to any drug not approved for sale in the country in which it is being used.
- Participation in a study using an investigational agent or non-drug therapy that may interfere with the conduct of this protocol (except study 213560)
- Anti- Tumor Necrosis Factor (TNF) or anti-IL-6 therapy (e.g., adalimumab, etanercept, infliximab, certolizumab, tocilizumab, golimumab).
- All biologics (e.g., rituximab, abatacept, interleukin-1 receptor antagonist).
- Janus kinase (JAK) inhibitors.
- Intravenous immunoglobulin (IVIG).
- IV cyclophosphamide (oral cyclophosphamide is permitted).
- Plasmapheresis, leukapheresis.
- Any live or live attenuated vaccines. (Participants who require a live or live attenuated vaccine during the study should have belimumab discontinued prior to receiving the vaccine).

Medication Category	Rule
All Prohibited Medications	Capture any of the Prohibited Medication subcategories below.
Other investigational agents	If ATC code contains "V98". If CMDECOD contains "ANIFROLUMAB". If CMDECOD contains "INVESTIGATIONAL DRUG",
Participation in a study using an investigational agent or non-drug therapy that may interfere with the conduct of this protocol	Requires clinical review to decide if treatment failure.
Anti-Tumor Necrosis Factor (TNF) or anti-IL-6 therapy	If LISTCODE = 30000417N or 332753.

Medication Category	Rule
All biologics	If LISTCODE = 30000417N or 332753.  If CMDECOD contains "RITUXIMAB", "ABATACEPT", "ANAKINRA", "BELIMUMAB", "ADALIMUMAB", "ETANERCEPT", "INFILIXIMAB", "CERTOILIZUMAB", "TOCILIZUMAB", "GOLIMUMAB".
Janus kinase (JAK) inhibitors	If LISTCODE = 30001836N.
Intravenous immunoglobulin (IVIG)	If LISTCODE = 332743.
IV cyclophosphamide	If CMDECOD = "CYCLOPHOSPHAMIDE" and CMROUTE="INTRAVENOUS".
Plasmapheresis, leukapheresis	If CMDECOD contains "PLASMAPHERESIS" or "LEUKAPHERESIS".

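### The prohibited-medication table counts any belimumab record with no period split, so standard care after Week 12 is mixed with on-treatment violations; some nearby coding rules also need correction

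*SAP*

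**What the plan says.** **Prohibition.** Protocol 6.8.2 opens its list with "The following medications and therapies are prohibited at any time during the study". The list includes all biologics and "IV cyclophosphamide (oral cyclophosphamide is permitted". The stated consequence of starting one is that belimumab stops and the participant leaves the study. Protocol 6.6 says that after Week 12 or early withdrawal "the participant will follow standard of care for SLE as determined by the investigator". Protocol 4.4 gives two end points: "A participant is considered to have completed the study if he/she has completed treatment phase (12 weeks) of the study", but "The end of the study is defined as the date of the last assessment (16-week post-treatment follow-up) of the last participant in the study".

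**Coding rules.** In SAP 6.2.7 the row for all biologics uses two list codes and a set of name strings. One string is BELIMUMAB; two others are printed "INFILIXIMAB', 'CERTOILIZUMAB". The IV cyclophosphamide row reads "If CMDECOD = 'CYCLOPHOSPHAMIDE' and CMROUTE='INTRAVENOUS". SAP 6.2.6, which serves the baseline table of allowable medication, classes a drug as an immunosuppressant if it is on list 333236 and not topical, or if its name contains CYCLOPHOSPHAMIDE "and the route of administration is 'ORAL' or 'PARENTERAL". Both sections end by stating that records are adjudicated, without saying how.

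**Tables.** SAP 6.1.4 gives the count and percentage of participants with prohibited medication and names no period. For concomitant medication in general it adds a summary for the on-treatment period. SAP 6.2.1 already defines pre-, on- and post-treatment periods by start date.

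**Follow-up.** In all three schedules of activities the concomitant-medication row is marked at the 8-week visit and blank at the 16-week contact. Footnote 2 limits that contact to adverse events and the pregnancy test. Protocol 6.8 requires every medication received during the study to be recorded. The additional AE and AESI analyses in SAP 4.3.2 and 4.3.2.1 pool treatment and follow-up.

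**The concern.** Participants enter because the investigator thinks they may benefit from belimumab (protocol 5.1), and the IV form is approved for children in China (protocol 2). Resuming it after Week 12 is therefore a realistic form of standard care. The SAP would enter such a participant in the prohibited-medication table beside someone who took a second biologic during the 12 treatment weeks. A reader of the study report could not tell the two apart from the table, and might take ordinary follow-up care for poor conduct on treatment.

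The other items are smaller. Read literally, the cyclophosphamide and biologic rules can leave a prohibited record unflagged. A biologic restarted between the 8-week and 16-week contacts is less reliably captured, so late follow-up adverse events are harder to relate to it.

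**Working it through.** No sample-size or power figure bears on this point. The check applies the written rules literally.

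**1. Belimumab after Week 12.** Take a participant who finishes the 12 weeks and then receives commercial belimumab.
- Protocol 6.6: allowed for, as the investigator's standard care.
- Protocol 6.8.2: belimumab is a biologic, and the study runs to the 16-week assessment (4.4), so on its wording the prohibition applies. Its consequence (stop belimumab, withdraw) does not fit someone who has already completed under 4.4.
- SAP 6.2.7: the name contains BELIMUMAB, so the record is flagged.
- SAP 6.1.4: the participant is counted, with no period shown.
- SAP 6.2.1: the start date would place the record in the post-treatment period, but the table does not use that classification.

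**2. Cyclophosphamide.** Outcome by recorded name and route:

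| Name and route | Allowable by the 6.2.6 cyclophosphamide clause | Prohibited by 6.2.7 |
|---|---|---|
| Exact name, ORAL | yes | no |
| Exact name, INTRAVENOUS | no | yes |
| Exact name, PARENTERAL | yes | no |
| Longer name, INTRAVENOUS | no | no |

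The first two rows agree with protocol 6.8.2. The third can hide an IV dose, and the fourth fails because 6.2.7 needs an exact name where 6.2.6 needs only containment. That either record type will occur is an assumption. Separately, if list 333236 includes cyclophosphamide (its contents are not given), the non-topical clause of 6.2.6 would admit even a record coded INTRAVENOUS as allowable at baseline.

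**3. Biologic strings.** The protocol names eight biologics as examples: adalimumab, etanercept, infliximab, certolizumab, tocilizumab, golimumab, rituximab and abatacept. Six contain a SAP string; infliximab and certolizumab do not.

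**4. The 16-week contact.** The medication row is blank at V18 (weekly dosing), V14 (10-day dosing) and V12 (two-weekly dosing), which is the 16-week contact in each schedule. Adverse events are collected there.
- With contacts at 8 and 16 weeks after last dose, the stretch without a scheduled check is 112 − 56 = 56 days, or 56/112 = 50% of follow-up.
- With ±7 days on each contact it runs from 105 − 63 = 42 to 119 − 49 = 70 days.
- If time is counted from the last scheduled dose (Day 78, 71, 71) to the SAP's 16-week target (Day 197, 193, 197), the shares are 56/119 = 47%, 56/122 = 46% and 56/126 = 44%.

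These figures describe calendar spacing. They do not measure bias.

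**5. Size per participant.** 1/17 = 5.9 percentage points, if the planned 17 (described as approximate) are all treated.

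**6. Link to the primary analysis.** The primary estimand (protocol 3) uses PK data only up to the start of a prohibited medication. The last scheduled PK sample is at Day 81 or 85 (protocol 8.5, Table 2), so items 1 and 4 come too late to touch it. Items 2 and 3 could matter only if the separate PK analysis plan (SAP 4.2) takes its exclusions from these flags, which the documents do not say.

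**The case against.** The best defence is that the strings are a first screen. Records are adjudicated. The study team tracks protocol deviations and reviews them before database freeze (SAP 6.1.3). Reasons for withdrawal are tabulated (SAP 6.1.1), and concomitant and prohibited medication are listed by participant. The anti-TNF row relies on list codes that may hold infliximab and certolizumab whatever the spelling in the next row, and a text-extraction error in those spellings cannot be fully excluded. This stands, and it makes the practical effect of the cyclophosphamide and spelling faults probably small.

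It is also fair that a table without periods follows a prohibition worded to cover the whole study, and that the protocol itself plans the pooled safety analysis as an addition to the on-treatment one. But adjudication would not cure the belimumab count: an adjudicator applying the written prohibition would confirm the record. The pooled analysis is legitimate; what it lacks is a mark on events that follow a restart.

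A reader might infer that the SAP's prohibited rule for cyclophosphamide contradicts the protocol. It does not: the IV rule in 6.2.7 agrees with protocol 6.8.2. The weakness is in the wider 6.2.6 rule and the different name match. A reader might also infer that medication started late in follow-up need not be recorded. Protocol 6.8 requires it, and protocol 10.3.3 has concomitant therapy considered in causality assessment. What is missing is a scheduled prompt.

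**Conclusion.** The point holds as a minor one. Its core is the undated BELIMUMAB string together with a prohibited-medication table that has no period, set against a protocol that leaves unclear whether the prohibition covers follow-up. Confidence in the reading of those rules, and of the blank schedule entry, is high. Confidence that the cyclophosphamide and spelling faults would change a result is lower, because adjudication and unseen list codes may catch the records.

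The effect is on descriptive outputs: the prohibited-medication table, the baseline allowable-medication table and the additional 28-week AE and AESI summaries. How many participants would be affected cannot be derived from the documents.

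It would be tempting to conclude that the primary PK estimand or the on-treatment safety endpoint is compromised. The documents do not show this. Nor do they rule out a route to the PK estimand, since it depends on identifying prohibited-medication starts and the source of that identification is not stated.

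**What to change.** **In the SAP** (wording and minor programming):
- Tabulate prohibited medication separately for the on-treatment and post-treatment periods of SAP 6.2.1.
- In the AE and AESI listings already planned, flag follow-up events with onset after a recorded biologic restart.
- Correct the two misspelled strings, after checking the source file.
- Use the same containment match for cyclophosphamide in 6.2.6 and 6.2.7.
- In 6.2.6, remove PARENTERAL or query such records for the actual route, and exclude IV cyclophosphamide from the list 333236 clause. Removing PARENTERAL alone may leave IV use classed as allowable.
- State whether the PK analysis plan uses these flags.

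**In the protocol** (an amendment with ethics approval, protocol 10.1.1):
- Reconcile 6.6, 6.8.2 and 4.4 on the period of the prohibition. Which rule applies is for the sponsor to decide.
- Reconcile the blank 16-week entry with 6.8, for example by adding a medication question with start date to the existing contact.

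If no amendment is made, the SAP corrections are still worth making on their own.
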